### **C.5. Phlebotomy and Blood Processing at the CCI**

Standard methods for phlebotomy and blood processing will be used. Red blood cells and plasma will be stored in 1 ml container at -170 degree freezer until assay measurements. All assays will be performed by a qualified laboratory selected based on quality of their work and competitive pricing bids (i.e., [name] laboratory at the University of Minnesota or [name] lab at Tufts University, Boston).

### **C.6. Assessment of Digital Pulse Amplitude**

Study subjects will be asked to refrain from caffeine-containing beverages or tobacco consumption 12 hours prior to the measurement of endothelial function. Digital pulse amplitude will be measured in the fasting state (as outlined above) with a fingertip peripheral arterial tonometry (PAT) device (Endo-PAT2000, Itamar Medical, Caesarea, Israel) in a supine position after a minimum of 20 minute rest in a quiet room with controlled temperature (20-23 degree Celsius). Details on digital pulse amplitude measurements have been published elsewhere. Briefly, the PAT device contains a pneumatic plethysmograph, which applies a uniform pressure to the surface of the distal index finger, thereby allowing measurement of pulse volume changes in the finger. Baseline pulse amplitude will be measured from each finger tip for about 5 minutes. The arterial flow will then be interrupted for 5 minutes with a cuff placed

on a proximal forearm with an occlusion pressure equal to the highest value of 200 mm Hg or the subject's systolic blood pressure plus 60 mm Hg. The contralateral arm (dominant arm) will serve as control. Lack of residual pulsatility will be monitored throughout the occlusion period. Pulse amplitude will be recorded electronically in the test and control fingers and analyzed by a computerized and automated algorithm that provides the average pulse amplitude for each 30-second interval after forearm cuff deflation up to 4 minutes (Itamar Medical). The change from the baseline measurement will be expressed as the reactive hyperemia index (RHI), which in part reflects vasodilator function of the digital microcirculation. Previous studies have demonstrated that RHI is to a large part dependent on nitric oxide bioavailability.

For statistical analysis, we will calculate the pulse amplitude response to hyperemia for each 30-second interval as a ratio of the post-deflation pulse amplitude to the baseline pulse amplitude as described previously. The RHI will be computed by dividing the ratio obtained on the test side (side with blood pressure cuff) over the ratio obtained on the control finger. Since the peak of the RHI has been shown to occur between 90 and 120 seconds after the cuff release, we will use the average of RHIs obtained at 90 and 120 seconds post deflation for analysis. The reproducibility of this technique has been described previously. RHI is correlated with traditional brachial ultrasound and CVD risk factors. Low RHI has been associated with CAD events and improve CAD prediction beyond traditional risk factors.

In order to preserve blinding of key personnel, the PI will complete the assessment of endothelial function and an independent research assistant will share the assignment group with the study subject once all activities of study visit # 2 have been completed and PI and other staff have left the CCI. The RA will instruct the subjects assigned to Vascepa on how to obtain the study drug at the BWH research pharmacy. Furthermore, during the third visit, the RA will see all study subjects before any blinded staff and collect Vascepa bottle with remaining capsules when applicable. This way, the possibility that the PI or study staff inadvertently sees the Vascepa bottle is minimized. Subjects will be reminded not to disclose their group status to study staff other than the RA assigning the group.

### **C.7. Laboratory Assays**

In a random sample of 5 subjects in each arm, we will measure fatty acid profile at visit # 2 and visit # 3 to assess compliance with EPA intervention. The fatty acid profile will be measured in plasma using the method previously described by Cao et al. For the extraction of plasma phospholipid fatty acids, 0.3 mL of plasma is mixed with 0.7 volume of 0.9% saline. Then, 50 uL of 2 g/L 17:0 standard (diheptadecanoyl phosphatidylcholine) is added to monitor the extraction efficiency. Lipids are extracted from plasma with a mixture of chloroform:methanol (2:1, v/v), and cholesterol, triglycerides and phospholipid subclasses are separated on a silica thin-layer chromatography plate in a solvent mixture of petroleum ether, diethyl ether, and glacial acetic acid (80:20:1, v/v/v). The band of phospholipids is harvested for the formation of methyl esters. Fatty acid methyl esters are prepared with 1.5 mL of 14% boron trifluoride in methanol, incubated at 80°C for 90 minutes, and extracted with petroleum ether. The final product is dissolved in heptane and injected onto a capillary Varian CP7420 100-m column with a Hewlett Packard 5890 gas chromatograph (GC) equipped with a HP6890A autosampler. The GC is configured for a single capillary column with a flame ionization detector and interfaced with HP chemstation software. Fatty acid methyl esters from 12:0 through 24:1n9 are separated, identified and expressed as percent of total fatty acids. The following coefficients of variation were obtained on 20 blind duplicates: linoleic acid = 2.6%; ALA= 2.4%; arachidonic acid = 2.4%; EPA= 3.3%; docosapentaenoic acid (DPA) = 2.9% and DHA= 2.7% at [name] laboratory at the University of Minnesota (one of our collaborative laboratories).

Plasma hsCRP will be measured by Sandwich enzyme linked immunosorbent assay (ELISA). Plasma oxidized LDL and plasma ET-1 will be measured using a commercially available sandwich-enzyme immunoassay kit (R & D);

All samples will be labeled with the date of collection, subject ID, and visit #. Since blood samples will be processed and stored in subzero freezer by the CCI lab personnel, PI and study staff as well as lab personnel measuring assays will be blinded from the drug assignment.

A summary of major steps of the study is provided below (**Table 3**).

**Table 3.** Time points for activities during the study period

Activities	Study Week		
	-4 to -1	0	12
Prescreening via telephone	x		
Measurement of triglycerides	x		
Final screening visit	x		
Random allocation to EPA or no EPA and study diary		x	
PAT measurements (endothelial function) and phlebotomy	x	x	x
Demographics, height, weight, medical history, food questionnaire		x	x
Blood pressure and biomarkers (OxLDL, ET-1, and hsCRP)		x	x

### **C.8. Data Management**

Our team has developed a sophisticated computer system to create and maintain data sets. Out-of-range, internally inconsistent, and unclear data will be reviewed and corrected as necessary. Data collected during each visit will be double-entered into the database system. All data will undergo additional within-form and across-time checks to verify accuracy. This database will be maintained on a UNIX server that is backed up nightly, ensuring at least two current copies at all times. Data entry is performed by two different study staff with many years of experience in data processing. The two generated files will be compared. Any errors in coding or keying will be corrected promptly. Access to the network is password-protected to assure confidentiality.

### **D. Approach to Achieve Proposed Aims**

#### **D.1. Main Aim:      **Effects of EPA on endothelial function in adults with diabetes and hypertriglyceridemia****

Initially, descriptive statistics such as the minimum, maximum, median, mean and standard deviation for each continuous variable and frequency table for each categorical variable will be used to summarize the data as well as detect outliers, data entry mistakes, and missing values. Exploratory graphical techniques such as Boxplots, Histograms, Quantile-Quantile plots, and Stem and Leaf plots will be used to further examine these data. The normality of the distribution of primary outcome of interest will be examined with a normal probability plot. The differences of baseline characteristics between EPA and placebo groups will be assessed using two sample t-tests, Chi-square tests or other non-parametric tests as appropriate. The primary analysis will be a comparison of the change in RHI from baseline to post-intervention between the 2 groups of subjects randomized to either 4g/d of EPA or no drug using a two sample t test or Wilcoxon rank-sum test. Analyses will follow the intention-to-treat principle although compliance adjusted analysis will be explored where applicable.

In addition, we will develop a general linear model including treatment and gender as the main effects, and the interaction term between treatment and gender. We will also examine

confounding by age, gender, blood pressure, smoking, exercise, body mass index, and alcohol consumption. However, due to limited sample size of this pilot study, we will evaluate each covariate separately, and the final adjusted model will include no more than 5 predictors.

We expect an increase in RHI in the EPA group compared with the control group. The main goal is to estimate this effect size in order to properly design the future confirmatory trial. A lack of statistical significance in this pilot study could be due to several possibilities: 1) four grams per day of EPA do not influence endothelial function in this population; 2) unbalanced distribution of other determinants of digital pulse amplitude that we were unable to control in this pilot study biased the findings; a future larger study would address this issue; 3) lack of effect may be attributable to inadequate power to detect a smaller improvement in endothelial function; such concern will not be an issue in the main trial with adequate statistical power. We will calculate nutrients and energy intake from food questionnaires and assess any change in dietary patterns during the study period (by comparing post- and pre-nutrients). All analyses will be completed by blinded staff and unblinding will only occur when primary and secondary analyses are completed.

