## **C.4. Study Visits**

**Visit # 1:** During this visit, the PI will explain the study objectives, study protocol, and sequences of events and answer any remaining questions that the subject may have about the study. If after such conversation with the PI, the subject is still willing to freely participate in the study, then he/she will sign the informed consent prior to the beginning of the screening process. Specifically, subjects will obtain overview of the study and the PI will complete endothelial function assessment using EndoPat2000 device. Subjects with RHI of 2.0 or less will be eligible and will be asked to provide blood sample for triglyceride measurement. First visit will end with the collection of blood specimen and subjects will be told that the coordinator will notify them via telephone of the results for further eligibility. Only subjects with triglycerides between 150 and 400 mg/dl will be eligible to be invited to the second study visit.

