**Visit # 2:** Eligible subjects identified during visit # 1 will be asked to the CCI fasting but will be allowed to take their usual morning medications. Subjects will be instructed to start fasting at 8PM of the night before the study visit. Pregnancy test will be done to rule out pregnancy among pre-menopausal women without history of surgical sterilization. For subjects randomized to Vascepa, women who can become pregnant during the study will be asked to use a contraceptive method (i.e., hormone, intrauterine device, barrier, or abstinence) during the study and six months after the final visit. During the second visit, we will collect baseline blood samples (20 ml) for measurement of biomarkers (hsCRP, ET-1, and oxLDL); other relevant biomarkers (i.e., TNF $\alpha$ , NTproBNP, apoC3, apoA5, galectin 3, free fatty acids, relevant single nucleotide polymorphisms, and fatty acids will be measured at a later time upon securing new funding on stored blood specimens). Resting blood pressure and pulse will be measured (2x) after 15 minutes of rest and information on age, sex, race, education, height, weight will be collected. Subjects will also complete a Willett food frequency questionnaire to assess their baseline diet. Digital pulse amplitude measurements (see C.6. below) will be done. A dedicated research assistant (RA) will discuss the randomization scheme provided by the statistician with the subjects. The RA will not be blinded to the treatment assignment. Otherwise, PI, study coordinator, statistician, and other staff at the lab measuring biomarkers will all be blinded. Subjects randomized to Vascepa will know that they are taking the drug containing omega-3, since the drug is not disguised and there is no placebo (open label trial). The RA will advise subjects not randomized to Vascepa (control subjects) to continue their usual habits. Each subject randomized to EPA will receive a 12-week supply of study EPA from the BWH pharmacy with the instructions to take 4 g/d. Each subject will receive a study diary to record potential adverse effects during the next 12 weeks. Enrolled subjects will be contacted by telephone once a month by the coordinator to query about potential adverse effects and remind them of the upcoming final visit.

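### Free improvement: adjust the primary RHI comparison for week-0 RHI, which is already measured but is not a planned covariate

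*Combined protocol and SAP*

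**What the plan says.** Section D.1 sets the primary analysis: "The primary analysis will be a comparison of the change in RHI from baseline to post-intervention between the 2 groups of subjects randomized", carried out "using a two sample t test or Wilcoxon rank-sum test". A further general linear model contains treatment, gender and their interaction. D.1 will also examine "confounding by age, gender, blood pressure, smoking, exercise, body mass index, and alcohol consumption", one covariate at a time, and adds that "the final adjusted model will include no more than 5 predictors". Week-0 RHI enters only as the value subtracted in the change score; it is not among the model terms or the candidate covariates. D.2 carries the same approach to the biomarkers and does not mention the baseline value, though it does not rule it out.

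The measurement is available. At Visit 2 (C.4), "Digital pulse amplitude measurements (see C.6. below) will be done", and Table 3 (C.7) schedules "PAT measurements (endothelial function) and phlebotomy" at screening, week 0 and week 12. Under C.6 the research assistant will "share the assignment group with the study subject once all activities of study visit # 2 have been completed", so week-0 RHI precedes knowledge of the arm.

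D.1 and D.3 both say that the pilot is mainly meant to estimate the effect size, in D.3 with its standard error, so that a confirmatory trial can be sized.

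**The concern.** Randomisation makes the change-score comparison valid, so nothing here is an error. The issue is precision. A change score assumes that one unit of week-0 RHI predicts exactly one unit of week-12 RHI. When the true slope is lower, the subtraction adds noise. ANCOVA estimates the slope and removes that noise.

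With 15 subjects per arm, precision is what the pilot has least of. A wider interval than necessary around the effect size passes directly into the planning of the confirmatory trial.

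**Working it through.** **Inputs.** From C.3 and D.3: n = 15 per arm, SD 0.4, effect size 1.05, power 80%. Not stated, so assumed: two-sided alpha 0.05; ρ, the week-0/week-12 correlation among analysed subjects (0.3 to 0.9); k, the week-0 SD divided by the week-12 SD (0.8 to 1.1). D.3 does not say whether 0.4 is the SD at one visit or the SD of change.

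**1. The plan's own figure.** Read 1.05 as standardised, that is 1.05 × 0.4 = 0.42 RHI units. The noncentrality is 1.05 × √(15/2) = 2.88 on 28 df, and power is 79.3%, in line with the stated 80%. Read as raw RHI units, 1.05 would give about 100%, so the standardised reading is the one intended.

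**2. Variances of the treatment difference**, with s the week-12 SD:

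- Change score: (2/n) s² (k² + 1 − 2ρk)
- ANCOVA: (2/n) s² (1 − ρ²) × [1 + 1/(2n − 4)]; at n = 15 the bracket is 27/26, the average cost of estimating the slope with normal data
- Ratio, ANCOVA to change: (1 − ρ²)(27/26) / (k² + 1 − 2ρk)

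For k = 1 this reduces to (1 + ρ)/2 × 27/26. At ρ = 0.5 it is 0.75 × 1.038 = 0.779. It reaches 1 at ρ = 25/27 = 0.926. Simulation (60,000 trials per correlation) gave 0.779 at ρ = 0.5, 0.882 at 0.7 and 1.012 at 0.95, against 0.779, 0.883 and 1.013 from the formula.

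| Variance ratio | ρ 0.3 | 0.5 | 0.7 | 0.8 | 0.9 |
|---|---|---|---|---|---|
| k = 1.1 | 0.61 | 0.70 | 0.79 | 0.83 | 0.86 |
| k = 1.0 | 0.68 | 0.78 | 0.88 | 0.93 | 0.99 |
| k = 0.9 | 0.74 | 0.86 | 0.96 | 1.01 | 1.04 |
| k = 0.8 | 0.81 | 0.93 | 1.02 | 1.04 | 0.99 |
| 30 subjects worth (30/ratio, k = 1.0) | 44 | 39 | 34 | 32 | 30 |

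The change score is as good or better for ρ of about 0.78 to 0.96 at k = 0.9, and 0.65 to 0.89 at k = 0.8. For k above √(27/26) = 1.019, ANCOVA is better at every ρ.

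**3. Bound on the loss.** Since k² + 1 − 2ρk = (1 − ρ²) + (k − ρ)², the ratio can never exceed 27/26. The worst loss is 1/26 = 3.8% of variance, whatever ρ and k.

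**4. Power for a true difference of 0.42** (noncentral t; ANCOVA on 27 df, averaged over chance baseline imbalance).

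| | ρ 0.3 | 0.5 | 0.7 | 0.8 | 0.9 |
|---|---|---|---|---|---|
| 0.4 = SD of change: t test | 79% | 79% | 79% | 79% | 79% |
| ANCOVA, k = 1.0 | 92% | 88% | 84% | 82% | 80% |
| ANCOVA, k = 0.8 | 87% | 82% | 78% | 78% | 80% |
| 0.4 = SD at each visit (k = 1.0): t test | 65% | 79% | 95% | 99% | 100% |
| ANCOVA | 81% | 88% | 97% | 99% | 100% |

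With 0.4 as the SD of change and k = 1.0, the mean 95% CI half-width falls from 0.30 to 0.24, 0.26, 0.28 and 0.29 at ρ = 0.3, 0.5, 0.7 and 0.8. There is no material gain at 0.9.

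**5. Effect of screening.** C.4 provides: "Subjects with RHI of 2.0 or less will be eligible and will be asked to provide blood sample for triglyceride measurement". Selecting on low RHI 1 to 4 weeks before week 0 could make the week-0 SD smaller than the week-12 SD, the less favourable direction for ANCOVA. It also lowers ρ. In 24 assumed scenarios (truncated-normal screening RHI, unselected SD 0.4, mean 1.7 to 2.1), k was 0.82 to 0.97 and ρ was 0.22 to 0.84. The variance ratio stayed between 0.67 and 0.98.

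**6. Skewed RHI** (simulated lognormal data, equal SDs, ρ = 0.3 to 0.9 as above). With skewness 0.7, ANCOVA power is 92%, 88%, 84%, 82% and 80%, against 78% for the rank-sum test. With skewness 1.75, ANCOVA gives 91%, 88%, 85%, 84% and 82%, against 80% for the t test. The rank-sum test gives 85 to 86% and overtakes ANCOVA from ρ = 0.7. ANCOVA's type I error was 5.2% with normal data and 4.5 to 4.6% with skewness 1.75.

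**The case against.** The strongest reply is that the planned test is sound, the trial is an exploratory pilot, and the size of the benefit is unknown. C.6 leaves reproducibility to cited work, and no correlation is given. At ρ near 0.9, or at k = 0.8 with ρ of 0.7 to 0.8, there is nothing to gain or a little to lose. This stands as a limit on the expected gain. It does not remove the case for changing, because the loss is bounded and small.

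Second, D.1 checks normality and allows a rank-sum test, whereas a single ANCOVA on untransformed RHI takes that choice away. Under heavy skew with ρ of 0.7 or more, the rank-sum test is more powerful, and the 3.8% bound does not cover that comparison. This also stands, and is why the rank-sum test should stay as a named sensitivity analysis. A rank-sum p-value alone, however, does not supply the effect size and standard error that D.3 asks for.

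Third, the power figures depend on what 0.4 means. If it is the single-visit SD, the power gain is larger at ρ = 0.3 (65% to 81%) and nearly nil from 0.8. The variance ratios are the same under either reading.

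Fourth, the bound assumes 15 analysed per arm. C.2 recruits 33 to protect that number; at 13 per arm the bound would be 1/22 = 4.5%.

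**Conclusion.** The point holds as a recommended improvement, not as a defect. Week-0 RHI is collected on everyone before assignment is disclosed and is named as a covariate nowhere. With equal SDs and 15 per arm, adjusting for it reduces the variance of the main estimate for any correlation below about 0.93. The reduction is large at low to moderate correlation (32% at 0.3, 22% at 0.5), small at 0.8 (7%) and about nil at 0.9. Against the change-score mean difference, the loss cannot exceed 3.8% of variance at 15 per arm with normal data. The algebra is certain; the gain in this trial is not, because the correlation, the SD ratio and the skewness are all assumptions.

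**What to change.** In D.1, before unblinding, replace the primary-analysis sentence with wording such as:

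> Week-12 RHI will be compared between arms by ANCOVA with week-0 RHI and gender, the stratification factor, as covariates. The adjusted mean difference, its SE and 95% CI are the primary result. The SD of RHI at each visit, the observed week-0/week-12 correlation, the SD of change and the residual SD will be reported for sizing the confirmatory trial. The Wilcoxon rank-sum test on change is a sensitivity analysis.

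If the blocks within ethnicity described in C.3 are kept, two ethnicity indicators can be added. Treatment, week-0 RHI, gender and the two indicators make five terms, which meets the D.1 cap but leaves no room for other covariates or the treatment-by-gender term in that model. In D.2, use the same baseline-adjusted form for hsCRP, ET-1 and oxLDL, with any transformation applied at both visits.

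The cost is SAP wording and no new data. Week-0 RHI and gender take one degree of freedom each. Adding gender changed simulated power by no more than about 0.3 percentage points, and adding two balanced ethnicity indicators as well cost at most 0.8 points.

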## **C.3. Randomization Scheme**

Randomization will occur during the second study visit at the CCI for those who meet eligibility criteria. In this pilot study, 30 subjects will be randomized with equal probability to EPA intervention (n=15) or no EPA (no drug) (n=15) stratified according to gender. Permuted blocks (block size of 2) will be used to achieve groups of equal size. We will create blocks within each gender and each ethnicity (Caucasian, African- American, and others) to assure balance distribution of gender and ethnicity between the two groups.

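### The primary RHI comparison ignores the gender and ethnicity strata used to randomise, so the t-test's standard error is too wide to the extent that those factors predict change in RHI

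*Combined protocol and SAP*

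**What the plan says.** C.3 describes the strata in two ways. It first names gender alone: "stratified according to gender. Permuted blocks (block size of 2) will be used". It then says "We will create blocks within each gender and each ethnicity", with three ethnicity categories, in order "to assure balance distribution of gender and ethnicity between the two groups". On the second description there are up to 6 strata for 30 subjects.

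D.1 states: "The primary analysis will be a comparison of the change in RHI from baseline to post-intervention between the 2 groups of subjects", "using a two sample t test or Wilcoxon rank-sum test". Neither test uses the strata. As a further step, "we will develop a general linear model including treatment and gender as the main effects, and the interaction term between treatment and gender". The plan will also examine "confounding by age, gender, blood pressure, smoking, exercise, body mass index, and alcohol consumption", and "the final adjusted model will include no more than 5 predictors". Gender is in both the extra model and the list; ethnicity is in neither.

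D.2 follows the same approach for the biomarkers and mentions an adjusted regression without naming its covariates. D.1 and D.3 describe the study as a pilot whose main purpose is to estimate the effect size (D.3 adds its standard error) so that a confirmatory trial can be sized. No section explains why the primary comparison leaves out the factors used to randomise.

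**The concern.** Blocking within strata removes most between-stratum variation from the treatment contrast. A pooled t-test leaves that variation in its residual variance. It therefore reports a standard error larger than the true sampling error of the estimate, and its type I error falls below the nominal level. The rank-sum test is conservative for the same reason, but it yields no standard error, so the SE point applies to the t-test only.

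The condition is that gender or ethnicity predicts **change** in RHI. A stable difference in RHI level between strata cancels in the change score and costs nothing. No bias and no excess of false positives is at stake. What is at stake is the accuracy of the standard error that the pilot exists to supply, and some power.

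**Working it through.** **Inputs from the documents.** 15 subjects per arm, blocks of 2, strata by gender and three ethnicity categories (C.3); SD 0.4, effect size 1.05, power 80% (D.3).

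**Assumptions.** Two-sided 5% level (not stated). The SD of 0.4 is taken as the SD of change in RHI (D.3 does not say). The share of the variance of change explained by the strata (R²) is not given, so a range of 0 to 30% is shown. The gender and ethnicity mix is not given, so two mixes are shown.

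**Step 1: the plan's own figure.** Read as a standardised difference, 1.05 corresponds to 1.05 × 0.4 = 0.42 RHI units. The noncentral t with 28 df gives power of 79.3%, which agrees with the stated 80%. Read as a raw RHI difference, 1.05 would give more than 99.9%, so the standardised reading is the one intended.

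**Step 2: the mechanism.** The unadjusted SE is 0.4 × √(2/15) = 0.146. With perfect balance within strata the true SE would be 0.146 × √(1 − R²), so the reported SE would be too wide by a factor 1/√(1 − R²): 1.00, 1.05, 1.12 and 1.20 at R² of 0, 10, 20 and 30%. Incomplete blocks in small strata leave some imbalance, so the actual factor is slightly smaller and was simulated.

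**Step 3: simulation.** Blocks of 2 within gender × ethnicity with incomplete blocks allowed, N = 30, additive effects, half of R² from gender and half from ethnicity (pattern 0, 1, −0.5), 10,000 trials per cell. The adjusted model has treatment, gender and ethnicity indicators, with ethnicity levels pooled at a minimum count of 4. Mix A is gender 50/50, ethnicity 60/25/15. Mix B is 70/30 and 80/12/8. The third block of rows assumes gender is the only stratum (50/50) and the only predictor, with 12,000 trials per cell.

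| Strata | Quantity | R² 0% | 10% | 20% | 30% |
|---|---|---|---|---|---|
| Mix A | Reported SE / true SE, t-test | 1.00 | 1.05 | 1.10 | 1.17 |
| | Type I error %, t-test | 5.2 | 3.9 | 3.3 | 2.5 |
| | Type I error %, rank-sum | 4.9 | 3.5 | 2.9 | 2.1 |
| | Type I error %, adjusted | 5.4 | 4.7 | 5.0 | 4.9 |
| | Power % at 0.42, t-test / adjusted | 79 / 79 | 80 / 82 | 80 / 85 | 83 / 90 |
| Mix B | Reported SE / true SE, t-test | 1.00 | 1.04 | 1.10 | 1.15 |
| | Type I error %, t-test / adjusted | 5.0 / 5.1 | 4.2 / 5.1 | 3.6 / 4.8 | 2.6 / 4.1 |
| | Power % at 0.42, t-test / adjusted | 79 / 79 | 80 / 82 | 81 / 85 | 82 / 88 |
| Gender only | Type I error %, t-test / adjusted | 5.0 / 5.0 | 3.7 / 4.8 | 2.7 / 4.7 | 2.3 / 5.1 |
| | Power % at 0.42, t-test / adjusted | 80 / 80 | 80 / 83 | 81 / 87 | 82 / 91 |

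In mix A at R² of 20%, the t-test reports an SE of 0.146 against a true 0.133; the adjusted model reports 0.133 against 0.132. A separate simulation with a 65/20/15 ethnicity mix and no pooling gave t-test SEs too wide by about 1, 6, 11 and 17% at the same four R² values.

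**Step 4: effect on the next trial's size.** At 80% power, carrying the pilot's unadjusted SD forward inflates the sample size as follows.

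- Next trial stratified, analysed unadjusted: (2.802 / (1.960 + 0.842 × √(1 − R²)))² − 1 = 0, 3.2, 6.7, 10.6%.
- Next trial stratified and adjusted: 1/(1 − R²) − 1 = 0, 11.1, 25.0, 42.9%.

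The documents do not say how that trial will be analysed.

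**Step 5: the pilot's own noise.** With 28 df, the 95% interval for the variance runs from 28/χ²(0.975) = 0.63 to 28/χ²(0.025) = 1.83 times the estimate.

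**The case against.** The size rests wholly on assumptions. Nothing in the documents shows that gender or ethnicity predicts change in RHI, and at R² of zero the adjusted model loses about 1 point of power. The plan as written is valid: the estimate is unbiased, type I error does not exceed nominal beyond simulation error, and t-test power stays at 79 to 83%. D.1 already has a model with gender. Ethnicity adds little beyond it: at R² of 10 to 30%, going from treatment plus gender to the full model gains 0.9 to 3.0 points of power in mix A and 0.1 to 1.1 in mix B. Even the largest inflation, 43%, lies inside the pilot's variance uncertainty (up to 1.83 times). If the next trial were neither stratified nor adjusted, the unadjusted SD would be the right input. Four terms also leave only one of the five permitted predictors for other covariates.

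Most of this stands as a limit on weight, and it rules out any claim of invalidity. It does not remove the point. The gender model is secondary and carries an interaction, so it does not directly give the overall effect and SE. The error runs in one direction, whereas sampling noise does not. The trade is also uneven: about 1 point of power lost at R² of zero, against about 4 to 7 gained at 20 to 30%. Making the rank-sum test a supporting result loses little for the pilot's main purpose, since it supplies no standard error.

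**Conclusion.** The concern holds. The primary analysis does not use the factors the trial randomises by, and ethnicity is in no stated D.1 model. The t-test's SE is about right if the strata explain none of the variance of change, and about 4 to 5%, 10% and 15 to 17% too wide if they explain 10, 20 and 30%. The error is conservative. At 10% or less it is small beside the pilot's own uncertainty. These sizes depend on the assumed R², subject mix and effect pattern, and on reading 0.4 as the SD of change. If C.3 means gender only, the ethnicity part falls away but the primary test still omits gender. The change is worth making because it is nearly free and bears on the pilot's declared main output, not because the planned test is invalid.

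**What to change.** 1. In C.3, state once whether the strata are gender only or gender and ethnicity.
2. In D.1, take the overall effect, SE and confidence interval from one pre-specified linear model for change in RHI, with treatment and the actual stratification factors as main effects: gender, plus two ethnicity indicators if ethnicity is a stratum. That is at most 4 predictors, within the cap of 5.
3. Fix a pooling rule based on counts alone before outcomes are seen. For example: if either of the two ethnicity levels other than Caucasian has fewer than 4 randomised subjects, combine those two; if the combined level is still below 4, omit ethnicity.
4. Keep the unadjusted t-test or rank-sum test as a supporting result and the treatment-by-gender interaction as exploratory. Use the same model in D.2.

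**Cost.** Wording only, since sex and race are already collected at Visit 2 (C.4). The critical t moves from 2.048 (28 df) to 2.060 (25 df). If the strata predict nothing, power at 0.42 falls from 79.5% to 78.7% in mix A and from 79.5% to 78.8% in mix B, or by about 0.1 to 0.2 points if gender is the only stratum. In mix A the four-predictor model breaks even at R² of about 3%. Pooling at a count of 4 would be triggered in about 35% of trials in mix A and 91% in mix B. The simulated results for the adjusted model already include this, and it is consistent with the model staying slightly conservative in mix B at R² of 30% (type I error 4.1%). One predictor remains under the cap for further adjustment.
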